2.5. CLINICAL STUDIES WITH COVID-19

FNC-Hope1 was a randomized, open-label, controlled clinical trial to evaluate the safety and efficacy of AZVUDINE tablets in the treatment of COVID-19, conducted at *People's Hospital of Guangshan County*, China.

Twenty individuals with COVID-19 with mild to moderate symptoms were randomly and equally assigned to 2 groups, experimental and control. Subjects who received conventional treatment with FNC + (no antiviral drugs) after diagnosis **reduced** the time to become nucleic acid negative for the first time by -7.3 days, compared to those who received conventional treatment alone (9.8). Subjects who received conventional treatment + FNC (no antiviral drugs) reduced the time to nucleic acid

negative for the first time by -6.8 days compared to those who received conventional treatment alone (11,30).

[figure not shown]

Figure 3: Kaplan-Meier curves of two consecutive negative tests for SARS-CoV-2 (a) first and b) second) in FNC and control group. Data are percent (%). Differences between groups were using the Log-rank test (Mantel-Cox)

On the fourth day after treatment, the rate of the first negative nucleic acid conversion reached 100% in patients in the FNC group and 30% in patients in the control group. Kaplan-Meier curves indicate the significant difference (p = 0.0013). On day 6, the negative conversion rate of the second nucleic acid reached 100% in patients of the FNC group and 40% in patients of the control group. Kaplan-Meier curves indicate the significant difference (p = 0.0011).

Regarding the safety analysis, there was no adverse event in the experimental group and three adverse events in the control group with an incidence of 30% (3/10) during the study period. All adverse events were grade 2 and were followed up until they disappeared. There were no serious adverse events, serious adverse reactions, major adverse events, or death events during the study period. The demographics and baseline characteristics of the subjects were similar and the proportions between the 2 groups were relatively balanced and comparable.

In 3 other hospitals in China, during the periods February 14 to March 10, March 1 to March 22, and March 7 to March 30, 32 volunteers with mild to severe symptoms were treated with different antiviral therapeutic approaches, including Arbidol,

Lopinavir/Ritonavir, Interferon, Hydroxychloroquine, Osetalmivir, Ribavirin, traditional Chinese medicine drugs, and others, prior to the start of AZVUDINE 5mg administration. Some volunteers received an attack dose of 10mg on the first day. After starting AZVUDINE treatment, concomitant with some different combinations of these antiviral drugs, the coronavirus viral load detection test became negative within 2-10days for 31 volunteers. One patient reported nausea and vomiting on the first day of AZVUDINE treatment and another patient had hypokalemia two days after AZVUDINE administration. Both completed the treatment. One patient dropped out of treatment, but no further AEs were reported from these and other patients. There were no serious adverse events (SAEs) or death events during the study period.

As of January 20, 2022, 262 patients (expected enrollment is 342 patients, for the phase III study - Hope 4 and except for the last 3 patients who entered the group last, all other patients have been cured and discharged. Considering a 27% dropout rate, 250 patients are sufficient to prove superior efficacy (125 patients per group), so statistical analysis will be completed once participants are discharged and completing the study at the end of follow-up.

The adverse reactions in this study were mainly ALT and AST increase, mainly grade 1 adverse reaction, only 1 case of ALT elevation was grade 3 adverse reaction, and the outcome was normalization, and the adverse reactions were common adverse reactions of antiviral drugs. No unexpected adverse reactions occurred.

2.6. RISKS AND BENEFITS

2.6.1. **Risks**

The participant's health condition may remain the same, improve, or worsen, and there is the possibility of adverse effects occurring during the study. The procedures that will be performed throughout the research period may present some minimal risks related to the clinic visits, including, but not limited to, possible minor bruising due to

blood sampling for laboratory analysis, anxiety due to questioning about health status, and side effects due to the use of the AZVUDINE drug.

Like all medicines, **AZVUDINE** can also cause some adverse reactions. The main reactions reported in preliminary studies with the **4mg** dose (**fever**, **headache**, **dizziness**, **nausea**, **vomiting**, **and diarrhea**) were mild to moderate in intensity. Studies with a loading **dose of 10 mg and maintenance with 5 mg showed a good safety profile**. As the doses may overload the renal and hepatic systems, special attention will be paid to the exclusion criteria, and for the participants included in the study, there will be monitoring of liver and kidney function for intervention if necessary. Should even minimal adverse reactions occur, the research team will be available to provide all necessary assistance.

2.6.2. Benefits

There may be no benefit in participating in the study, but in any case, we believe that the search for an effective and safe therapeutic option is fundamental and a priority, and so it is necessary to conduct a randomized study along the lines of this proposal. However, since this drug has already been shown to be effective in patients with COVID-19 (with the conversion of the viral nucleic acid to negative in a shorter time), a potential direct benefit to participants receiving AZVUDINE during the study can be expected. Patients in the PLACEBO group will have the assistance recommended for treatment of COVID-19, and all participants will have disease follow-up through monitoring, consultations, and testing.

2.6.3. Analysis of risks and benefits

Phase I and II clinical studies have provided a safety profile for the use of AZVUDINE in HIV-positive volunteers at doses up to 4 mg. *In vivo* studies have shown safety at doses at least 1000 times higher than those used in Phase I and II studies. Adverse reactions observed with 4mg of AZVUDINE were mainly fever, headache, dizziness, nausea, vomiting, and diarrhea, and the intensity of these AEs was mild to moderate.

Preclinical testing for carcinogenesis and reproductive toxicity has shown that the doses used in the clinic are significantly lower than the doses that showed toxic effects in these trials. No EAGs have been reported in the 48-week clinical trials conducted with AZVUDINE. However, because it is a nucleoside analog, there is a risk for fetal malformation, underscoring the importance of the exclusion criteria and follow-up of couples of childbearing age included in the study.

Preliminary studies conducted with volunteers with COVID-19 used doses of 5 mg of AZVUDINE and some volunteers received a loading dose of 10 mg of AZVUDINE. The data from these studies showed a good safety and efficacy profile relative to patients previously treated with other therapeutic approaches, where there was no conversion of viral nucleic acid to negative and no improvement in the clinical picture. In volunteers, after AZVUDINE administration, the two consecutive viral nucleic acid tests were negative and all patients were discharged. The AEs reported were mild disappearing without medical intervention and no EAGs occurred.

It is important to note that the loading doses may overload the renal and hepatic system due to increased metabolism and excretion of the drug. Given of this risk, special attention should be paid to the eligibility criteria, and for research participants included in the study, it is important that monitoring of liver and kidney

function be performed in the first few days, so that intervention can take place if necessary.

A potential direct benefit to participants who receive this drug during the study can be expected to be the conversion of the viral nucleic acid to negative in a shorter time. It is important to note some risks and benefits attached to the randomized trial model, such as the possibility of the research participant being allocated to the PLACEBO group, i.e., without intervention of the experimental drug, which may be a promising treatment, but is not yet available in clinical practice. However, participants in the PLACEBO group will have the assistance recommended for treatment of COVID-19, and all participants will have constant monitoring of the progress of the disease through consultations and examinations. In addition, participation in a clinical trial requires greater availability of the study participant, as there is a need for frequent follow-up.

There will be an intensive follow-up of the patient in the hospital unit. The evaluations will be made by trained professionals and any alterations will be identified and appropriate actions will be taken to minimize and/or recover them. In addition, the participant will have access to and guidance regarding all the tests performed. At any time, the participant may have access to all information obtained about him or her from this study, or about the overall results of the study after its termination. Withdrawal and/or termination of the trial will not affect the medical care offered to the participant, as control visits are scheduled.

All medical information will be confidential and only the study team will have access to avoid a breach of confidentiality. At no time will the participant's name or any information about their health be provided to anyone other than the study team. The information will be confidential and used only for the purpose of this research. All reasonable measures to avoid breaching the participant's identity and confidentiality will be taken. These include access to study documents only for those on the research team,

storage of printed documents in a locked file in a location with restricted access, and storage of electronic data in a database with secure access via individual username and password only for the researchers and other members of the research team.

By proving the clinical efficacy and safety of AZVUDINE, society will be able to benefit from an effective treatment against the new coronavirus.

2.7. JUSTIFICATION

The coronavirus emerged in late 2019, and since then it has been spreading around the world with high speed. In March, the World Health Organization declared a pandemic of the new coronavirus, a result of the high spread of this virus worldwide. Brazil is currently the second country with the highest number of cases, exceeding 200,000 deaths from COVID-19 (WHO, 2020e). As a consequence, the coronavirus has not only led to a large number of deaths to date but has also overburdened the health care system and impacted the economy worldwide and in Brazil.

A key strategy in the treatment of COVID-19 would be to find an effective, antiviral agent that leads to a reduction in viral load and, consequently, a reduction in the physiological damage caused by the coronavirus. Clinically approved drugs or drugs in advanced stages of development for the treatment of other viral diseases, such as HIV, should be considered for the treatment of SARS-CoV-2.

AZVUDINE is an antiviral drug that was developed for the treatment of HIV, and its safety and clinical efficacy have been demonstrated in HIV-positive patients. Clinical development of this drug is currently in phase III in China. Also, in vitro studies have shown that AZVUDINE has effective antiviral activity against SARS-CoV-2, and preliminary clinical trials conducted in China have also shown potential efficacy and safety of AZVUDINE in patients with COVID-19.

The number of cases and deaths from COVID-19 has been increasing worldwide and in Brazil in recent months. It is necessary to quickly find alternative therapies to control the complications of SARS-CoV-2 infection, since the development, immune response, and recovery from the disease caused by this virus are still uncertain.

This study aims to generate rapid, robust, documented evidence on the potential clinical efficacy and safety of AZVUDINE, for patients infected with SARS-CoV-2.

3. HYPOTHESIS

AZVUDINE has a therapeutic potential and safety profile for the treatment of patients with pneumonia caused by SARS-CoV-2.

4. OBJECTIVES AND OUTCOMES OF THE STUDY

Primary Objectives	Primary Outcome	
To evaluate the efficacy and safety of AZVUDINE (FNC) versus placebo in patients infected with moderate to severe stage SARS-COV-2;	 Proportion of participants with clinical status improvement [Period: until D15, approximately 14 days]. The criterion for a participant to have an improvement in clinical status is a decrease on the WHO Clinical Improvement Ordinal Scale in at least one category compared to screening (WHO, Jun/2020). 	

Secondary Objective	Secondary Outcome	
To evaluate the clinical	Proportion of participants with a clinical outcome of cure	
outcome between the	during the study; [Period: until D15, D21, and D28,	
AZVUDINE (FNC) group	approximately 14-30 days].	
versus placebo in	 The clinical endpoint of cure is defined in this 	
patients infected with	protocol as the absence of viral RNA in	
moderate to severe stage	collected samples and clinical conditions for	
SARS-COV-2;	hospital discharge ⁴ .	
,	• Time to normalization of body temperature (below 37.6°C	
	axillary); [Period: until D15, D21 and D28, approximately	
	14-30 days]	
	• Time to improvement of diarrhea, myalgia, fatigue,	
	malaise, cough, dyspnea, and headache; [Period: until	
	D15, D21, and D28, approximately 14-30 days].	
	• Changes in liver and kidney function baselines, and	
	inflammatory and immunological markers: [Period: until	
	D15, D21 and D28, approximately 14-30 days]	
	 Lab tests performed on days D1, D3, D5, D7, 	
	D9, D13, D15, D21, D28, and D60.	
	• Evaluation of the time to negative conversion of the	
	SARS- CoV-2 viral load by RT-PCR between AZVUDINE	
	(FNC) group and control group; [Period: until D15, D21	
	and D28,approximately 14-30 days].	
	Evaluation of the number of cycles for the detection of	
	SARS-CoV-2 viral load by RT-PCR and application of the	

⁴ According to the WHO Working Group on Characterization and Clinical Management of COVID-19 Infection (July, 2020), clinical and virological absence of infection (non-detectable RT-PCR) is suggestive of CURE for initially infected participants.

standard curve for viral load calculation; [Period: until D15, D21 and D28, approximately 14-30 days].

- Analysis of the relationship between the calculated viral load and the clinical progress of participants in the AZVUDINE (FNC) group compared to the control group; [Period: until D15, D21 and D28, approximately 14-30 days].
- Time and proportion of lung imaging improvement during treatment (Pattern of ground-glass opacities, mosaic paving, alveolar consolidation, reticular pattern/septal thickening, opacity with inverted halo, pleural/pericardial effusion, fibrosis and/or lymphadenomegaly); [Period: until D15, D21 and D28, approximately 14-30 days].
- Time of improvement and proportion of respiratory symptoms and signs during treatment (Lung rales, cough, sputum, sore throat); [Period: until D15, D21, and D28, approximately 14-30 days].
- Time to normalization of O2 saturation (above 95%);
 [Period: until D15, D21 and D28, approximately 14-30 days].
- Time to normalization of respiratory rate to levels ≤ 24rpm, in room air; [Period: until D15, D21 and D28, approximately 14-30 days]
- Frequency of supplemental oxygenation or non-invasive ventilation; [Period: until D15, D21 and D28, approximately 14-30 days].
- Frequency of invasive mechanical ventilation or extracorporeal membrane oxygenation (ECMO); [Period: until D15, D21, and D28, approximately 14-30 days].

- Proportion of moderate cases that progressed to severe cases requiring intensive care unit (ICU) care; [Period: until D15, D21, and D28, approximately 14-30 days].
- Length of hospital stay; [Period: until D15, D21 and D28, approximately 14-30 days].
- Occurrence of drug interactions; [Period: until D15, D21 and D28, approximately 14-30 days].
- Frequency and intensity of adverse events; [Period: until D15, D21 and D28, approximately 14-30 days].
- Frequency and intensity of unexpected adverse events;
 [Period: until D15, D21 and D28, approximately 14-30 days].
- Frequency and intensity of serious adverse events;
 [Period: until D15, D21 and D28, approximately 14-30 days].
- All-cause mortality rate during the study; [Period: until D15, D21 and D28, approximately 14-30 days].
- Evaluate the tolerability of AZVUDINE (FNC) use at 5mg/day regimen for up to 14 days: [Period: until D15, approximately 14 days].
 - Calculating treatment adherence;
 - Total time of use of AZVUDINE (FNC);
 - Proportion of participants who withdrew consent;
 - Proportion of participants who dropped out of treatment.

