	Safety follow-up will be performed at 28 and 60 days after				
	discharge. For the Early Termination (ET) of treatment, participants should follow the routine from visit 17: End of Treatment (D15), in advance. The study will be considered completed when the last				
	participant completes his or her last visit.				
	Individuals with the following characteristics will be				
	included in this study:				
	Age ≥18 years, regardless of gender;				
	2. Patients hospitalized in moderate to severe stages in				
	line with the Ministry of Health classification ¹ ;				
	3. Positive diagnostic test for SARS-CoV-2 by molecular				
INCLUSION CRITERIA	amplification of the virus in RT-PCR diagnosed from				
	respiratory specimen (nasopharyngeal, oropharyngeal,				
	lower respiratory tract [e.g., sputum]) collected <96				
	hours before randomization;				
	4. Time between symptom onset and inclusion ≤14 days;				
	5. Hospitalization within 48 hours of study inclusion;				
	6. Availability for follow-up during the study period;				

Mild: Flu-like syndrome (cough, sore throat or runny nose), followed or not by: Anosmia (olfactory dysfunction) Ageusia (gustatory dysfunction), Runny nose, Diarrhea, Abdominal pain, Fever, Chills, Myalgia, Fatigue, Headache;

Moderate: Persistent cough + daily persistent fever or Persistent cough + progressive worsening of another symptom related to COVID-19 (adynamia, prostration, hyporexia, diarrhea) or at least one of the above symptoms + presence of a risk factor.

Severe: Severe acute respiratory syndrome - influenza syndrome presenting: Dyspnea/respiratory distress or persistent chest pressure or $_{02}$ saturation less than 95% on room air or bluish coloration of lips or face.

 $^{^{\}mathrm{1}}$ The Brazilian Ministry of Health classifies the symptoms of COVID-19 into:

	7. Voluntary adherence to participate in the study and				
	signing the Informed Consent Form.				
	Individuals with one or more of the following characteristics				
	will not be eligible to participate in this study:				
	1. Patients known or suspected to be sensitive to				
	AZVUDINE or excipients (inactive ingredients:				
	microcrystalline cellulose, hydrated lactose,				
	polyvinylpyrrolidone K30, croscarmellose sodium,				
	magnesium stearate);				
	2. Patients diagnosed with pneumonia caused by other				
	pathogens;				
	3. Patients with liver disease (total bilirubin ≥2mg/dL,				
	ALT/TGP and AST/TGO ≥5 times above normal limit); ²				

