- Time to normalization of respiratory rate to levels ≤ 24rpm, in room air; [Period: until D15, D21 and D28, approximately 14-30 days]
- Frequency of supplemental oxygenation or non-invasive ventilation; [Period: until D15, D21 and D28, approximately 14-30 days].
- Frequency of invasive mechanical ventilation or extracorporeal membrane oxygenation (ECMO); [Period: until D15, D21, and D28, approximately 14-30 days].
- Proportion of moderate cases that progressed to severe cases requiring intensive care unit (ICU) care; [Period: until D15, D21, and D28, approximately 14-30 days].
- Length of hospital stay; [Period: until D15, D21 and D28, approximately 14-30 days].
- Occurrence of drug interactions; [Period: until D15, D21 and D28, approximately 14-30 days].
- Frequency and intensity of adverse events; [Period: until D15, D21 and D28, approximately 14-30 days].
- Frequency and intensity of unexpected adverse events; [Period: until D15, D21 and D28, approximately 14-30 days].
- Frequency and intensity of serious adverse events; [Period: until D15, D21 and D28, approximately 14-30 days].
- Taxa de mortalidade por todas as causas durante o estudo; [Período: até o D15, D21
 e D28, aproximadamente 14-30 dias]
- Evaluate the tolerability of AZVUDINE (FNC) use at 5mg/day regimen for up to 14 days: [Period: until D15, approximately 14 days].
 - Calculating treatment adherence;

- Total time of use of AZVUDINE (FNC);
- o Proportion of participants who withdrew consent;
- o Proportion of participants who dropped out of treatment.

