8.7. AE COLLECTION AND REGISTRATION

Any information relevant to the trial should be recorded from the first administration to the end of follow-up. AEs will be monitored throughout the study and the Principal Investigator, or someone deligated by him, will be responsible for recording all adverse medical events observed during the study, in detail, in the source documents and in each participant's eCRF, during the study period from the first dose to the end of follow-up, regardless of severity and causal relationship to the study drug.

All SAEs must also be recorded in eCRF as soon as they occur, and the information provided in the SAE report form must be consistent with the event-related data that is recorded in eCRF. All AEs, SAEs and special interest AEs must include the following content in detail:

• **Description:** Events should be described in medical terms, rather than the words used to record the participants' reports in the original document. If

applicable, symptoms, signs, laboratory abnormalities, and diagnosis should be included. If the same AE occurs more than once, in the same participant, and the participant recovered from both events, the AE should be recorded twice.

- Date of occurrence: the date when the AE first occurred in the participant or
 the date when the symptoms related to the AE occurred should be recorded. If
 the AE is the test result of an abnormal laboratory test or test with clinical
 significance, the date of occurrence is the date the test was performed.
- Date of result: the date of resolution of the AE-related symptoms should be recorded.
- AE intensity and severity: classified as: (1) mild, 2 (moderate), 3 (severe) or 4 (complete/severe impairment). ¹⁶
- Causal relationship between AE and study drugs: as per Table 5.
- Measures for the study drug: It should be recorded whether the participant
 continued using the drug or had to stop using it as a result of the AE or SAE. If
 the reaction occurred after the end of treatment, this item does not apply.
- Measures for AE: It should be recorded what measures were taken to solve the
 AE, such as drug therapy and/or non-drug therapy, hospitalization, surgery,
 among others. If no action was taken, this fact should be reported.
- **Outcome:** the disappearance of signs or symptoms; recovery with sequelae; stability; worsening; death; or loss to follow-up must be recorded.

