 Frequency and intensity of adverse events; [Period: until D15, D21 and D28, approximately 14-30 days]. 	Student's t-test / Mann-Whitney test / Pearson's chi- square test
 Frequency and intensity of unexpected adverse events; [Period: until D15, D21 and D28, approximately 14-30 days]. 	Student's t-test / Mann-Whitney test / Pearson's chi- square test
 Frequency and intensity of serious adverse events; [Period: until D15, D21 and D28, approximately 14-30 days]. 	Student's t-test / Mann-Whitney test / Pearson's chi- square test
 All-cause mortality rate during the study; [Period: until D15, D21 and D28, approximately 14-30 days]. 	Mann-Whitnoy tost

Evaluate the tolerability of AZVUDINE (FNC)
 use at 5mg/day regimen for up to 14 days:
 [Period: until D15, approximately 14 days].

 Calculating treatment adherence;
 Total time of use of AZVUDINE
 (FNC);
 Proportion of participants who withdrew consent;
 Proportion of participants who dropped out of treatment.

Student's t-test /
Mann-Whitney test /
Pearson's chi-square test

For safety analysis, AEs should be coded according to the MedDRA terminology dictionary (version 23.0) and the following criteria should be listed and analyzed:

- o Cases of EAs, EAGs, and of EAs leading to abandonment.
- Number and the rate of "normal to abnormal" or "abnormal worsening" of the laboratory and ECG indicator after the experiment.
- Laboratory indicator, ECG, abnormal physical examination cases and clinical interpretation.

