12.10. DEADLINE FOR COMPLETION OF THE STUDY

The estimated time from screening (Day -1 or Day 1) to the end of the study (last follow-up visits D60) for a participant is approximately 60 days. As a total timeframe for the study, approximately 7 (seven) months is estimated, after study approval by the Research Ethics Committee (CEP) and ANVISA, for completion and delivery of the Final Report.

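### The all-cause mortality and AE/SAE endpoints stop at D28 although follow-up and event recording run to D60, and the main SAE model states no window at all

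*Protocol*

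**What the plan says.** **Endpoint periods.** Section 4 lists "All-cause mortality rate during the study; [Period: until D15, D21 and D28, approximately 14-30 days". The synopsis, section 7.1.2 and the analysis table in section 11.3 repeat the same period. Section 7.1.2 sets the same limit for SAEs: "Frequency and intensity of serious adverse events; [Period: until D15, D21 and D28, approximately 14-30 days". All adverse events and unexpected adverse events are treated alike in these four places.

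**Follow-up and recording.** Section 12.10 describes "the end of the study (last follow-up visits D60) for a participant is approximately 60 days". Section 9.2 closes the study at the last participant's last visit. Section 8.7 requires events to be recorded "during the study period from the first dose to the end of follow-up, regardless of severity and causal relationship to the study drug". The synopsis states "Safety follow-up will be performed at 28 and 60 days after" discharge, and section 7.3 gives visit 20 (D60) the purpose of monitoring safety and efficacy.

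**Analyses without a window.** Under the primary objective, section 11.3 fits a logistic regression to the occurrence of SAEs and gives no time limit. The safety listings at the end of section 11.3 and the safety parameters in section 7.2 have none either. Section 8.1 makes death from disease progression reportable as an SAE.

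**The concern.** The mortality endpoint is titled as covering the whole study, but its period ends before the study does. The SAE endpoint ends at D28, while the SAE model that serves the primary objective has no stated end. The same death or SAE, on D40 for example, could therefore be an event in one analysis and not in another, depending on how the open window is read.

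Safety is half of the primary objective. With 90 participants per arm, fatal and serious events may be few, so the choice of window could affect the comparison. That choice should be fixed before unblinding. The protocol also asks participants to return for the D60 visit, yet no mortality, adverse event or SAE endpoint has a period that reaches it.

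**Working it through.** This is a comparison of time windows. The plan states no figure to reproduce, and nothing here depends on sample size or power.

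**1. Windows side by side**

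| Item | Where | Stated end |
|---|---|---|
| All-cause mortality | Synopsis; 4; 7.1.2; 11.3 table | D28 |
| AE, unexpected AE and SAE frequency | Same four places | D28 |
| SAE occurrence model (primary objective) | 11.3 | None |
| Safety listings | 11.3, end | None |
| Safety parameters | 7.2 | None |
| AE and SAE recording | 8.7 | End of follow-up |
| Last participant visit | 12.10; Table 10 | D60 |

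The first two rows conflict with the last two, and the middle three rows leave the matter open.

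**2. Size of the gap, start-of-treatment anchor.** Table 10 counts both D28 and D60 from the start of treatment.
- Gap = 60 - 28 = 32 days.
- Share of follow-up = 32/60 = 53%.
- With the ±3-day visit windows, the interval between the two visits is from (60 - 3) - (28 + 3) = 26 days to (60 + 3) - (28 - 3) = 38 days.

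**3. Other anchors.** The protocol does not keep to one anchor.
- The synopsis and section 5.1.1 count 28 and 60 days from discharge.
- Section 9.1 counts both from the end of treatment.
- Section 7 puts D28 two weeks, and D60 sixty days, after the end of treatment. The visit descriptions in section 7.3 use the same intervals from discharge.

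If both time points move together, as in section 9.1, the gap stays at 60 - 28 = 32 days. On the section 7 and 7.3 intervals it is 60 - 14 = 46 days. If the endpoint period means study day 28 and the last visit is 60 days after discharge, the gap is (discharge day + 60) - 28. Assuming discharge between D5 and D15:
- D5: 5 + 60 - 28 = 37 days.
- D15: 15 + 60 - 28 = 47 days.

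**4. Is the D60 information collected?** Section 8.7 says yes for adverse events and SAEs, and section 9.5 provides for searching public records and death certificates for participants who cannot be reached. But the section 7.3 procedure lists for visits 17 and 18 name adverse event monitoring, and those for visits 19 and 20 do not. A footnote to Table 10 leaves the D28 and D60 procedures to the investigator. The table's adverse event row is broken in the text available, so it cannot settle the point.

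**5. Laboratory endpoint.** Its period also ends at D28, yet its list of test days includes D60. Section 5.1.1 has blood samples taken at D28 and D60. The visit 19 and 20 lists name no blood sample except for the pregnancy test at visit 20.

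**The case against.** The strongest reply is that little is lost. The main safety analysis is the SAE model, and neither it nor the listings nor section 7.2 is cut at D28. Since deaths from progression are reported as SAEs, late deaths can enter there. A reader might infer that events after D28 are excluded from all safety analysis; the documents do not support that. This part of the objection stands. What remains is a D28 limit on the secondary endpoints beside an undefined window in the main model.

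Second, the bracketed period may be the operative definition, with the title merely loose wording. The cure endpoint has the same title phrase and bracket. A D28 mortality window is also acceptable in itself. Treatment lasts at most 14 days and the stated half-life is 13.8 hours, so day 28 from start of treatment leaves at least 28 - 14 = 14 days off drug. This stands against making D60 the main window, which would be a preference and not a correction. It does not explain why D60 safety follow-up appears in no mortality or SAE endpoint.

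Third, one might infer a count of missed deaths. The protocol gives no expected mortality for this population, and the earlier azvudine COVID-19 studies it describes reported no deaths, possibly in milder patients. No count can be supported, and zero late deaths is possible.

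Fourth, complete D60 data cannot be taken for granted, given the visit 19 and 20 procedure lists. This also stands, and the fix allows for it.

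**Conclusion.** The point holds in a limited form. The mortality and AE/SAE endpoint periods end at D28, while the protocol follows participants and requires event recording to D60. The SAE model and safety listings do not say which end applies. The uncovered span is 32 of 60 days on the Table 10 anchor. It stays at 32 days if D28 and D60 shift together, and reaches about 37 to 47 days if the endpoint period means study day 28 and D60 is counted from a discharge assumed to fall between D5 and D15.

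The number of events affected cannot be estimated from the documents. The primary efficacy endpoint, the sample size and the SAE reporting duties are untouched. This is a modest inconsistency on important outcomes that is cheap to remove before unblinding.

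**What to change.** - In the synopsis and sections 4, 7.1.2 and 11.3, keep D28 as a reported time point and add an end-of-study (D60) time point for all-cause mortality and SAEs.
- State the same end-of-study window for the SAE occurrence model in section 11.3.
- Use one anchor for D60 throughout; sections 1.1, 5.1.1, 7, 7.3, 9.1, 12.10 and Table 10 need to agree.
- Report by arm the number of participants with unknown vital status at D60.
- Reconcile the laboratory endpoint's D60 test day with its period ending at D28, and reconcile the visit 19 and 20 procedure lists with sections 5.1.1 and 8.7.

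The cost is wording changes and one extra summary, using event data that section 8.7 already requires. Some D60 data may be incomplete, which the vital-status count would make visible.
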